6.5. Baseline and Other Summaries and Analyses

6.5.1. Baseline Summaries

Baseline characteristics will include but may not be limited to the ones listed below and will be summarized descriptively. For continuous variables, the summary will include N (which is the number of subjects evaluable for the baseline characteristics), mean, median, SD and range (ie, minimum and maximum); for binary and categorical variables, the summary will include frequencies and percentages. A missing category will be included for those subjects with missing value. In addition to displays by treatment groups, the summaries will also be provided for all the treatment groups combined.

Demographic characteristics:

- Baseline age (2 categorizations: <18, ≥18 to ≤44, ≥45 to ≤64, ≥65 years; <18, ≥18 to ≤44, ≥45 to ≤64, ≥65 to ≤74, ≥75 to ≤84, ≥85 years; and continuous in years);
- Gender (Female, Male);
- Race (White, Black, Asian, Other);
- Geographic region (see [Section 6.4.1](#) for definition);
- Ethnicity (Hispanic/Latino, non-Hispanic/Latino);
- Baseline body weight (<60, ≥60 to ≤100, >100 kg; and continuous in kg);
- Baseline height (continuous in cm);
- Baseline waist circumference (continuous in cm);

- Baseline BMI (<18.5, ≥18.5 to <25, ≥25 to <30, ≥30 to <40, and ≥40 kg/m²; and continuous kg/m²);
- Baseline smoking status (Never Smoked, Former Smoker, Current Smoker);
- Duration of smoking started (continuous in years) for subjects who are Current Smokers or Former Smokers;
- Duration of smoking stopped (continuous in years) for subjects who are Former Smokers only;
- Baseline pack-year (continuous in pack-year) for subjects who are Current Smokers or Former Smokers;
- Baseline Alcohol use (Yes, No; continuous in units/week for subjects who have Current Alcohol use at Baseline); Yes is defined for subjects who have Current Alcohol use at Baseline, else No.

Baseline disease characteristics:

- Prior treatment history at randomization ("bDMARD-naïve", "TNFi-IR or bDMARD Use [Non-IR]") where prior treatment history is derived from the clinical database (see [Section 9.11](#)). Under the "TNFi-IR or bDMARD Use (Non-IR)" category, two subcategories: "TNFi-IR" and "bDMARD Use (Non-IR)" will be summarized. Subjects under "bDMARD Use (Non-IR)" are not TNFi-IR and have prior bDMARD Use without IR (see [Section 9.11](#));
- AS disease symptom duration (<5, ≥5 years; and continuous in years);
- AS disease duration since diagnosis (<5, ≥5 years; continuous in years);
- Family history of Spondyloarthritis (Yes, No);
- History of Uveitis (Yes, No);
- Current symptom of Uveitis (Yes, No) for subjects with history of uveitis;
- History of Psoriasis (Yes, No);
- Current symptom of Psoriasis (Yes, No) for subjects with history of psoriasis;
- History of Inflammatory Bowel Disease (IBD) (Yes, No);
- Current symptom of IBD (Yes, No) for subjects with history of IBD;
- HLA-B27 (Positive, Negative);
- Baseline hsCRP (≤2.87, >2.87 mg/L [ie, Elevated hsCRP]; and continuous in mg/L);

- Baseline metabolic syndrome (Yes, No) (see [Section 9.7.1](#) for definition);
- Baseline diabetes mellitus (Yes, No) (see [Section 9.7.2](#) for definition);
- Baseline PGA (continuous);
- Baseline Patient Assessment of Pain – Total Back Pain (continuous);
- Baseline Patient Assessment of Pain – Nocturnal Spinal Pain (continuous);
- Baseline BASFI (continuous);
- Baseline BASDAI Total score (continuous);
- Baseline Inflammation (Average of questions 5 and 6 of BASDAI) (continuous);
- Baseline BASMI and its 5 components (continuous);
- Baseline Spinal Mobility – Chest Expansion (continuous in cm)
- Baseline AS disease activity (ASDASCRP <1.3 [inactive disease], ≥1.3 to <2.1 [low disease activity], ≥2.1 to ≤3.5 [high disease activity], >3.5 [very high disease activity] units, and continuous) (van der Heijde et al. 2016; Machodo et al., 2018);^{9,10}
- Baseline presence of enthesitis based on MASES (Yes, No). Yes is defined for those subjects with Baseline MASES >0;
- Baseline MASES (continuous) for those subjects with Baseline MASES >0;
- Baseline presence of swollen joints (Yes, No). Yes is defined for those subjects with Baseline SJC(44) >0;
- Baseline SJC(44) (continuous) for those subject with Baseline SJC(44) >0;
- Baseline SF-36v2 – 8 domain scale (ie, norm-based), PCS, MCS scores (continuous);
- Baseline EQ-5D-3L – 5 dimension scores (continuous), EQ-VAS (Your own health state today) (continuous in mm) and EQ-5D-3L Utility score (UK) (continuous);
- Baseline FACIT-F – Total score, Impact domain and Experience domain scores (continuous);
- Baseline WPAI – 4 subscores (continuous in %);
- Baseline ASQoL Total score (continuous).

6.5.2. Prior and Baseline Treatments for Ankylosing Spondylitis

Prior use denotes any relevant drug use prior to Day 1. If there are missing values for any of the characteristics, add a “Missing” category to capture these subjects unless noted otherwise.

- Prior oral corticosteroids use (oral only: Yes, No, Missing is considered as No);
- Number of prior NSAIDs-IR (2 NSAID-IR, ≥ 3 NSAID-IR) for all subjects (see [Appendix Section 9.10](#) for definition of NSAID-IR);
- Number of prior TNFi-IR (1 TNFi-IR, 2 TNFi-IR) for subjects who have prior inadequate response to TNFi (ie, with prior treatment history of "TNFi-IR" derived from the clinical database, see [Appendix Section 9.11](#) for definition of TNFi-IR);
- Number of prior bDMARD Use (1 bDMARD Use, ≥ 2 bDMARDs Use) for subjects who are not grouped to "TNFi-IR" stratum but have prior bDMARD Use without IR (ie, bDMARD Use [Non-IR] derived from clinical database, see [Appendix Section 9.11](#)).

6.5.3. Concomitant Medications

Concomitant treatments are those treatments that are taken on Day 1 or after. These treatments can be summarized based on the periods of assessment and the summary will include only those subjects who received any concomitant medications post-baseline.

- Taken on Day 1 (at Baseline) only;
- Taken on Day 1 up to Week 16;
- Taken on Day 1 up to Week 48.

Concomitant medications for primary diagnosis:

- Concomitant csDMARDs (for any csDMARDs use [n, %] and for each csDMARD use, eg, Methotrexate, Sulfasalazine, etc. Full but non-exhaustive list of csDMARDs can be found in [Section 9.6 Table 7. List of DMARDs and NSAIDs](#)); Note that csDMARD is defined as non-bDMARD.
- Concomitant NSAIDs (for any NSAIDs use [n, %] and for each NSAID use. Full but non-exhaustive list of NSAIDs can be found in [Section 9.6 Table 7. List of DMARDs and NSAIDs](#));
- Corticosteroids (for any Corticosteroids use [n, %] and for each corticosteroid use, eg, Glucocorticoids);
- Pain Management/Analgesics (for any Pain Management/Analgesics use [n, %] and for each pain management/analgesics use).

6.6. Safety Summaries and Analyses

All the safety data will be summarized descriptively through appropriate data tabulations, descriptive statistics, and graphical presentations. AEs, vital signs, 12-lead ECG parameters, and laboratory tests will be summarized according to the Clinical Data Interchange Standards Consortium (CDISC) and Pfizer Standards (CaPS).

6.6.1. Adverse Events

AEs will be reported as treatment-emergent all causality and treatment-emergent treatment-related. A treatment-emergent AE is any event that starts on or after the first dosing day. The algorithm will not consider any events that start prior to the first dose date.

The relationship to study treatment is assessed by the investigator.

AEs will be displayed by two analysis periods: (1) Baseline to Week 16; and (2) Baseline to Week 48 (end of study including follow-up).

Tier-1 events, ie, AEs of special interest will be summarized descriptively.

Tier-2 events will be analyzed using asymptotic methods proposed by Miettinen and Nurminen (1985).¹¹ Risk ratios (tofacitinib 5 mg BID compared to placebo) and 2-sided 95% CI will be reported. P-values will not be reported for Tier-2 events. This analysis is applicable for the period of Baseline to Week 16 only.

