6. STUDY PROCEDURES

6.1. Screening

Subjects will be screened within 30 days prior to administration of investigational product to confirm that they meet the entrance criteria for the study.

Rescreening of subjects will be allowed in a limited number of circumstances as determined by the Pfizer Medical Monitor (eg, requires antimicrobial therapy within 2 weeks prior to the first dose of investigational product, requires emergency surgery) and should be confirmed with the Pfizer Medical Monitor when rescreening can occur.

The study investigator or a sub-investigator will discuss with each subject the nature of the study, its requirements, and its restrictions. Written informed consent/assent must be obtained prior to performance of any protocol-specific procedures.

Subjects, who are on prohibited medications and are deriving a beneficial response from the medication, should not be entered into this study. However, there may be subjects taking a prohibited medication who have experienced an ineffectual/suboptimal response or side effects and wish to enter the study. These subjects may require a washout period that extends beyond the screening duration. For these subjects, written informed consent and a unique subject number obtained through the IRT system must be obtained prior to initiation of the washout period. No other screening activities should be performed at this time. These subjects should return for a Screening visit within the allowed window, at which time all screening procedures should be completed.

At all visits, subjects should complete the “Patient Reported Outcome” (PRO) questionnaires at the clinic prior to any other study procedures outside of the informed consent process.

The following procedures will be performed:

- Informed consent;
- Collect demographic information (sex, date of birth, race, and ethnicity);
- ASAS/ASDASCRP Component: “Patient Global Assessment of Disease” (NRS), “Patient Assessment of Spinal Pain” which include Total Back Pain(NRS) and Nocturnal Spinal Pain (NRS), BASDAI (NRS), BASFI (NRS);
- Confirmation of diagnosis of active AS: based on the Modified New York Criteria for Ankylosing Spondylitis (1984) and BASDAI score of ≥ 4 and back pain score (BASDAI Question 2) of ≥ 4 ;

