8.1.4. Time Period for Collecting AE/SAE Information

The time period for actively eliciting and collecting AEs and SAEs (“active collection period”) for each subject begins from the time the subject provides informed consent, which is obtained before the subject’s participation in the study (ie, before undergoing any

study-related procedure and/or receiving investigational product), through and including a minimum of 28 calendar days after the last administration of the investigational product.

For subjects who are screen failures, the active collection period ends when screen failure status is determined.

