8.2.6. Hospitalization

Hospitalization is defined as any initial admission (even less than 24 hours) in a hospital or equivalent healthcare facility, or any prolongation of an existing admission. Admission also includes transfer within the hospital to an acute/intensive care unit (eg, from the psychiatric wing to a medical floor, medical floor to a coronary care unit, or neurological floor to a tuberculosis unit). An emergency room visit does not necessarily constitute a hospitalization; however, the event leading to the emergency room visit is assessed for medical importance.

Hospitalization does not include the following:

- Rehabilitation facilities;
- Hospice facilities;
- Respite care (eg, caregiver relief);
- Skilled nursing facilities;
- Nursing homes;
- Same-day surgeries (as outpatient/same-day/ambulatory procedures).

Hospitalization or prolongation of hospitalization in the absence of a precipitating clinical AE is not in itself an SAE. Examples include:

- Admission for treatment of a preexisting condition not associated with the development of a new AE or with a worsening of the preexisting condition (eg, for workup of a persistent pretreatment laboratory abnormality);
- Social admission (eg, subject has no place to sleep);
- Administrative admission (eg, for yearly physical examination);

- Protocol-specified admission during a study (eg, for a procedure required by the study protocol);
- Optional admission not associated with a precipitating clinical AE (eg, for elective cosmetic surgery);
- Hospitalization for observation without a medical AE;
- Preplanned treatments or surgical procedures. These should be noted in the baseline documentation for the entire protocol and/or for the individual subject.

Diagnostic and therapeutic noninvasive and invasive procedures, such as surgery, should not be reported as SAEs. However, the medical condition for which the procedure was performed should be reported if it meets the definition of an SAE. For example, an acute appendicitis that begins during the reporting period should be reported if the SAE requirements are met, and the resulting appendectomy should be recorded as treatment of the AE.

Severity Assessment

If required on the AE page of the CRF, the investigator will use the adjectives MILD, MODERATE, or SEVERE to describe the maximum intensity of the AE. For purposes of consistency, these intensity grades are defined as follows:

MILD	Does not interfere with subject's usual function.

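### SAP 6.6.1 defines treatment-emergent AEs by onset date alone, so an event that starts before Day 1 and later turns serious or stops treatment can be missing from the between-arm AE tables

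*SAP*

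**What the plan says.** SAP 6.6.1 sets the rule in two sentences. The definition is "A treatment-emergent AE is any event that starts on or after the first dosing day", and the exclusion is "The algorithm will not consider any events that start prior to the first dose date". Neither has an exception for later worsening, seriousness or discontinuation. The same section limits the reporting categories: "AEs will be reported as treatment-emergent all causality and treatment-emergent treatment-related". Two periods are displayed, Baseline to Week 16 and Baseline to Week 48.

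The protocol collects AEs over a longer span. Under Protocol 8.1.4 the active collection period "begins from the time the subject provides informed consent". Protocol 6.1 gives the usual length of the pre-dose part: "Subjects will be screened within 30 days prior to administration of investigational product". For subjects who need a longer washout of a prohibited drug, it adds that "written informed consent and a unique subject number obtained through the IRT system must be obtained prior to initiation of the washout period".

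Where severity is captured at all, the Severity Assessment text at the end of Protocol 8.2.6 has the investigator choose a grade "to describe the maximum intensity of the AE". That is one value per event.

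**The concern.** A subject can enter the treatment period with an AE already open, and it can become serious or stop treatment on drug. For an immunosuppressant, that deterioration is a harm the AE tables are read for. Under an onset-only rule, a single record with a pre-dose start date keeps the event out of both treatment-emergent categories and both analysis periods. Meanwhile the SAP's own disposition summary may show the same subject as stopping for an adverse event. The tables most readers use to compare arms could then disagree with the disposition table, with nothing in the SAP to explain the difference. Serious events and discontinuations are usually sparse, so even a few missing subjects would be noticeable.

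**Working it through.** No arithmetic applies, because the point is about a definition. The check sets the rules side by side and follows one event through them.

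1. **Can a pre-dose AE be in the database?** Yes. Collection starts at consent (Protocol 8.1.4). Screening runs up to 30 days (Protocol 6.1). For some biologics the required time off drug is 10 weeks (Protocol 5.8.1), and consent comes before a washout that outlasts screening. That longer exposure concerns a minority: about 80% of subjects are planned to be bDMARD-naïve (Protocol 3), and only those still on the drug at consent would wash out under observation.

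2. **Can such an event still be open at Day 1?** Yes, if mild. Protocol 4.2 excludes AST or ALT above 1.5 times the upper limit of normal at screening. It also excludes recent infections that needed antimicrobials, hospital care or parenteral therapy, or that the investigator considers clinically significant. A mild untreated infection or a smaller transaminase rise is not excluded.

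3. **Does the onset date move when the event worsens?** Only if the site opens a new record. No general rule tells sites to do so. Recording one maximum intensity per event fits a single record that keeps its first start date. Some provisions point the other way in part: examination changes since Day 1 are to be recorded as AEs (Protocol 7.1.4 and 7.1.4.1), and so are test results that lead to discontinuation or significant added treatment (Protocol 8.2.2).

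4. **Worked example.** A mild infection starts 10 days before the first dose, becomes serious at Week 6, and investigational product is stopped. The site keeps one record.

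| Output | Rule | Is the event there? |
|---|---|---|
| Treatment-emergent AE tables, both periods | SAP 6.6.1 | No: the start date precedes the first dose |
| Disposition summary before Week 16, by arm | SAP 6.1.2, Table 3 | Yes, if an adverse event is the reason given; no onset filter |
| SAE reporting | Protocol 8.1.4.1 | Yes |
| Serious-infection and withdrawal summaries | Protocol 9.3 | Planned with no onset limit; the SAP does not say whether its treatment-emergent filter applies |
| Laboratory tables by arm and visit | SAP 6.6.2 | Only what shows in laboratory values |
| Committee review | Protocol 9.6 | Only for the event types listed there |

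5. **Contrast.** The same infection starting on the first dosing day, even before the tablet is taken, is counted. So is a new record opened at Week 6.

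The definition therefore leaves the event out of the between-arm AE tables, while the disposition table can count the subject as stopping for an adverse event.

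**The case against.** The best defence is that the rule is clear and deliberate. The SAP version history attributes it to a sponsor data standard, and an onset-date rule avoids subjective calls about worsening. No two passages contradict each other. This stands, and it is a good reason not to demand a different definition.

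The recording premise also rests partly on sources that are not in the documents. CRF completion instructions or the sponsor standard cited in SAP 6.6 might require a new record, and the standard displays mentioned in SAP 3.5 might include these events. That too stands as a limit, which is why the event *can* be left out rather than always is.

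A reader might infer that these events go unreported. The documents do not support that: SAE reporting, Table 3, the Protocol 9.3 summaries, laboratory tables and adjudication capture many of them. None of these, however, puts the event back into the treatment-emergent AE comparison.

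A reader might also infer that the safety comparison is biased toward no difference. Randomization should balance events present before dosing, so a differential loss needs the drug to aggravate them. The documents give no evidence on that for this trial. What does not depend on it is some under-count of on-treatment harm in these tables whenever such an event occurs.

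**Conclusion.** The point holds as a limited gap in safety tabulation. An AE that starts between consent and Day 1, then becomes serious or leads to discontinuation on treatment, can be missing from the treatment-emergent tables, and the SAP provides neither a supplementary display nor a reconciliation.

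The size cannot be stated, because the documents give no rate of pre-dose AEs or of their worsening. A reader might assume that 20 to 30% of 120 subjects per arm have a pre-dose AE and 5 to 10% of those worsen. That gives 120 × 0.20 × 0.05 = 1.2 to 120 × 0.30 × 0.10 = 3.6 subjects per arm, which could then be set against the Tier-2 threshold of 4. Those rates have no basis in the documents. The comparison also fails: the result is a total over all terms, while SAP 3.5 applies the threshold to each Preferred Term.

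The conclusion assumes that at least some sites keep one record per event and that no unseen instruction overrides this. It is a cheap improvement to the plan, not a flaw in its efficacy conclusions or its safety surveillance.

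**What to change.** Keep the sponsor's standard definition and add the following to SAP 6.6.1:

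- A supplementary table by arm, for Baseline to Week 16 and Baseline to Week 48, of AEs with onset before the first dose that after it became serious or led to discontinuation of investigational product. Identify them from the SAE records and the Disposition – End of Treatment page.
- A statement that these events are included in the serious-infection and withdrawal summaries planned in Protocol 9.3.
- A reconciliation of AE-related discontinuation counts with Table 3 for the period before Week 16, explaining any subject who appears in one and not the other.

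Do not use the severity field to find these events. A single maximum-intensity value cannot show whether the maximum came before or after the first dose. The approach assumes that SAE records carry a usable date for when the event became serious. Linking a non-serious event to the Disposition page may need manual review of a few subjects.

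The cost is one extra display, a short SAP addition and slightly higher AE counts in the affected summaries. Dosing, stopping rules and the efficacy analyses do not change.
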